1.0 PROTOCOL SUMMARY AND/OR SCHEMA

Some patients treated with brain radiation therapy for tumors located in the head may develop new or increased enhancing mass lesions. These worsening lesions may represent radiation injury/necrosis or tumor progression. This study will examine the utility of MRI perfusion and FDG PET/CT to determine if the enhancing lesions represent radiation injury or tumor progression. Both MRI perfusion and FDG PET/CT scans are part of the standard of care for patients with indeterminate lesions after treatment. The purpose of this study is to prospectively enroll these patients in order to determine if MRI perfusion or FDG PET/CT performs better in predicting if a worsening enhancing brain lesion represents radiation injury or tumor progression. In addition the entire cohort analyses, subcohort analyses will be performed for patients belong to specific clinical scenarios and compared using an interaction test.

Prior to enrolling in the study, each patient will have a CT or MRI scan that shows an increasing indeterminate mass lesion. If the screening scan is a brain MRI perfusion, it can also function as the protocol intervention.

Screening (within 12 weeks of enrollment): Neurological and/or physical examination

Intervention: Brain MRI perfusion and PET/CT performed within 12 weeks of each other. Either MRI perfusion or PET/CT may be performed first. The first of the two scans should be performed within 12 weeks after the screening scan showing an increasing indeterminate mass lesion. If the screening scan is a brain MRI perfusion, it can also function as the protocol intervention. Imaging based diagnosis of radiation injury vs. worsening tumor will be rendered by a study neuroradiologist and by a nuclear medicine radiologist and entered into a secure database.

*Note that clinical reads of the MRI perfusion and PET/CT will be rendered as per the standard of care, usually within 24-48 hours after completion of the study. These reports get dictated in Powerscribe and then become part of the patient's electronic medical record.

Off study: Patients will remain on study until the completion of either the MRI perfusion or PET/CT that are within 12 weeks of each other. After one of these scans, the patient will have no active interventions and will be off study. Patients will obtain a standard of care brain MRI scan about every 2-3 months. These MRI scans will be used to track disease progression.

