2.0 OBJECTIVES AND SCIENTIFIC AIMS

The primary goal of the proposed study is to directly compare PET/CT with MRI perfusion in distinguishing between radiation injury and tumor progression. These are the two most commonly performed tests for possible radiation injury cases (MRI spectroscopy, diffusion imaging, and experimental PET/CT tracers trail far behind). There has been very little

comparative effectiveness research to determine an optimal imaging strategy, whether both are complementary and necessary, or whether one outperforms the other. This protocol will help us answer those questions, and may lead to dramatic changes in the way we and other institutions manage these diagnostic dilemmas. After the completion of radiation therapy and a follow-up MRI exam demonstrating a worsening enhancing brain lesion, patients will undergo both MRI perfusion and PET/CT exams. If the follow up MRI is a brain MRI perfusion, it will serve as both the screening scan and protocol intervention. In this case, patients will undergo only a PET/CT exam. The findings from each of these imaging studies will be used to predict whether the lesion represents tumor progression or radiation necrosis based on clinical follow-up and/or pathologic tissue sampling.

Primary Endpoint:

1. To assess the utility of PET/CT and MRI perfusion studies in predicting whether worsening enhancing brain lesions seen after radiation therapy represent radiation injury or tumor progression. This study will examine the role of these two imaging techniques in predicting diagnosis and treatment planning.

Exploratory Endpoint:

- 1. To assess the utility of PET and MRI perfusion studies in predicting tumor progression in patients with tumors with a history of brain radiation therapy receiving anti-angiogenic therapy (such as bevacizumab). Due to direct drug effects upon the vasculature, these tumors often show little or no enhancement despite clinical worsening and increasing non-enhancing abnormalities. The role of advanced imaging in determining progression in lesions that do not show increased enhancement has not been defined. In an exploratory fashion, we will enroll patients with tumors with a history of brain radiation therapy receiving anti-angiogenic therapy with suspected progression and increased nonenhancing lesions.

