7.0 ASSESSMENT/EVALUATION PLAN

7.1 Imaging evaluation

The maximal abnormalities on the MRI perfusion scans and PET/CT scans will be recorded according to standard ROI and volume of interest (VOI) measurements:

FDG PET/CT:

- 1. SUV_{lesion} (SUV=standardized uptake value)
- 2. SUV_{normal}
- 3. $SUV_{ratio} = SUV_{lesion}/SUV_{normal}$
- 4. PET texture factors: contrast, homogeneity, entropy, skewness, kurtosis
- 5. PET topological factors: eccentricity, solidity, and extent

(SUV=standardized uptake value)

MRI Perfusion:

- 1. V_P (plasma volume)
- 2. K^{trans} (volume transfer coefficient between plasma and extravascular extracellular space)

RSI Diffusion:

1. RSI Celluarity

Either PET/CT or MRI perfusion may be performed first, but both studies should be completed within 12 weeks of each other. The PET/CT will be interpreted by a study nuclear medicine radiologist while blinded to the MRI perfusion results. The MRI perfusion will be interpreted by a study neuroradiologist while blinded to the PET/CT results. Each MRI perfusion metric and each FDG PET/CT metric will be independently tested to predict the diagnosis of radiation injury vs. tumor progression. In addition to independently testing the utility of MRI perfusion and PET/CT in determining radiation injury, we will also examine if combining both techniques will perform better than either one alone.

The protocol proposes using the current standard of practice for diagnosing radiation injury vs. worsening tumor, in terms of histopathology (when available) or clinical and radiological follow up. We will also perform a subcohort analysis to determine if there is any difference between patients diagnosed by histopathology (anticipated at approximately 15-25%) vs. patients diagnosed by follow up.

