9.0 PRIMARY OUTCOMES

We will use the PET/CT and MRI perfusion to independently predict whether or not an increased enhancing lesion represents radiation injury or tumor progression. The diagnosis will be established by a neuro-oncologist and/or a radiation oncologist according to pathology results if available, or by clinical and radiological follow up after a minimum of 6 months. If diagnosis is rendered by follow up, then the clinician will review available chart records and imaging studies after blinding of the PET/CT and MRI perfusion results by a third party (e.g., research assistant). Based on clinical practice, we anticipate that approximately 18 patients will undergo repeat surgery and have pathological evidence of the diagnosis.

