11.0 BIOSTATISTICS

The purpose of this nonrandomized study is to test the predictive value of PET/CT and MRI perfusion in distinguishing radiation injury from tumor progression.

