11.1 Entire cohort analyses

Despite the heterogeneity of potential tumor types, radiation injury has a common mechanism in all patients: blood brain barrier disruption, inflammation, gadolinium contrast leakage into the interstitial space, and enhancement. In most clinical scenarios, we expect lower MRI perfusion and lower FDG PET/CT measurements for radiation injury regardless of the original tumor type. When considering the target accrual of 150 patients with indeterminate lesions, we anticipate that tumor progression will occur more commonly (approximately 90 patients) than radiation injury (approximately 42 patients) or uncertain diagnoses (approximately 8 patients). We anticipate that only 20-30% (28-42 patients) will require the entire 6 month follow up period to establish their diagnosis. Some patients may require >6 months and be followed up to 1 year to establish their diagnosis. Loss to follow up or death prior to determining a definitive diagnosis is expected to be uncommon (<5 patients). Unless an autopsy is performed to render a diagnosis for the brain lesion, death will be a criterion for removal from the study as described in Section 10.

We will perform one-sided two-sample t-tests (because previous analysis showed that MRI perfusion measurements are reasonably symmetric, have a small range and are usually lower in radiation injury than in tumor progression). To approximately assess the power of the analysis, we focus on the one-sided two sample t-test with the type I error

(claiming a difference while there is not) rate of 5%. With 150 patients over 2 years and assuming the effect size is 0.5 (meaning that the difference is half of the pooled standard deviation), type II error (failure to detect a difference that actually exists) rate is about 10%. If the effect size is 0.7, the type II error rate is about 1%. Here we used generic mean/standard deviation ratios because multiple measurements will be examined.

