An interim analysis is also planned at half of the expected total. An O'Brien-Fleming boundary will be used to ensure the type I error rate is not inflated. Specifically, this requires the p-value must be <0.0088 at the interim analysis to stop the trial early and declare statistical significance and <0.0467 at the final analysis to declare statistical significance. Moreover, if the interim analysis p-value is >0.50 then we will stop the trial and declare futility. Under null hypothesis (that tumor and necrosis cannot be differentiated by the new imaging method) the early stopping probability is 0.5 for declaring futility and is 0.0088 for declaring significance. Under the alternative hypothesis with the effect size of 0.7, the early stopping probability is 0.002 for declaring futility and is 0.69 for declaring significance.

To quantify predictive power of the MRI perfusion package, receiver operating characteristic (ROC) analyses will be used.

For the analysis of PET/CT, similar approaches will be used. To compare the predictive power of various MRI perfusion measurements and PET/CT measurements, ROC curves will be drawn, and the area under the curve (AUC) will be computed and compared among MRI perfusion and PET/CT measurements. Bootstrap confidence intervals will be constructed to establish confidence levels and the difference between the two AUCs will be calculated and examined whether it is significantly different from 0. Due to the multiple comparisons needed, a false discovery rate (FDR) approach will be employed to control for the family-wise error rate. The positive FDR approach will yield new quantities called q-values for making statistical inferences.^{53, 54} The purpose of implementing an FDR approach is to adjust the p-values from multiple tests (due to multiple MRI perfusion and PET/CT parameters to be examined).

For the exploratory objective to examine increasing non-enhancing masses, similar analyses will be done. We estimate 5-10 patients with recurrent tumors may receive antiangiogenic therapy. If the numbers are small, we will summarize the results descriptively and suggest future research directions. If the numbers are sufficient, we will perform similar sensitivity, specificity, ROC and AUC analyses.

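### The interim stops in section 11.1 end the whole trial on an unspecified tumor-versus-injury p-value, with no provision for the PET/CT-versus-MRI comparison, and the interim count contradicts itself (48 or 75)

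*Combined protocol and SAP*

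**What the plan says.** Section 2.0 states the aim as a comparison: "The primary goal of the proposed study is to directly compare PET/CT with MRI perfusion in distinguishing between radiation injury and tumor progression". Section 1.0 agrees; the purpose is to "determine if MRI perfusion or FDG PET/CT performs better in predicting if a worsening enhancing brain lesion represents radiation injury or tumor progression".

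The labelled primary endpoint in section 2.0 is different in kind: "To assess the utility of PET/CT and MRI perfusion studies in predicting whether worsening enhancing brain lesions". Section 9.0 follows it ("We will use the PET/CT and MRI perfusion to independently predict whether or not an increased enhancing lesion represents radiation injury or tumor progression"), and section 11.0 gives the statistical purpose as to "test the predictive value of PET/CT and MRI perfusion in distinguishing radiation injury from tumor progression". These concern how well each modality discriminates, not which is better.

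Section 11.1 bases its power statement on a one-sided two-sample t-test of tumor against injury at 5%. It justifies the test because "previous analysis showed that MRI perfusion measurements are reasonably symmetric, have a small range", and uses generic effect sizes because several measurements will be examined. The interim rule follows: "this requires the p-value must be <0.0088 at the interim analysis to stop the trial early and declare statistical significance", 0.0467 at the final analysis, and a futility stop above 0.50. The null is that the new imaging method, in the singular, cannot separate tumor from necrosis. PET/CT is then given similar approaches. The AUC difference between modalities is to be tested against zero, with no interim boundary and no power figure.

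On timing, section 11.1 first puts the look at half of the expected total. Its last paragraph puts it at 1 year or 48 subjects and calls 48 one half. Section 4.1 gives the target as 150 and reports 75 patients accrued over 2 years.

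**The concern.** A crossing answers whether some metric separates tumor from injury. It does not answer which modality is better, yet it ends recruitment for both. The paired AUC comparison, the combined decision rule and the subcohort analyses would then rest on about half the planned data, plus any patients enrolled while outcomes were pending.

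The rule also cannot be run without a further decision. Section 7.1 lists two MRI perfusion metrics and several PET metrics and says "Each MRI perfusion metric and each FDG PET/CT metric will be independently tested to predict the diagnosis of radiation injury vs. tumor progression". The plan does not say which of these p-values meets the boundary, or what happens if they disagree.

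Finally, two interim sizes are given with one pair of boundaries, and that pair belongs to only one of them.

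**Working it through.** **Inputs.** From section 11.1: one-sided 5%; interim 0.0088, final 0.0467; futility above 0.50; stated stopping chances at d=0.7 of 0.69 (efficacy) and 0.002 (futility); expected outcomes 90 tumor, 42 injury, 8 uncertain. These sum to 140, not 150, so the splits below are assumptions. From section 4.1: target 150; 75 accrued in 2 years.

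**1. The plan's boundaries.** For two looks at information fraction f, O'Brien-Fleming uses z₁ = c/√f and z₂ = c, with c solved so that P(Z₁>z₁ or Z₂>z₂) = 0.05 and corr(Z₁,Z₂) = √f.
- f = 0.5: z = 2.373 and 1.678, p = 0.0088 and 0.0467. The printed levels reproduce; overall error is 0.050 with futility not binding.
- f = 48/150 = 0.32: z = 2.920 and 1.652, p = 0.0017 and 0.0493. Using 0.0088/0.0467 here gives an overall error of 0.052.

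Half of 150 is 75. 48 is half of 96, which is not given as a target anywhere.

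**2. The plan's stopping chances.** The noncentrality is d√(mn/(m+n)). The efficacy chance is P(T > t at 0.0088) and the futility chance is P(T < 0), with T noncentral t on m+n−2 degrees of freedom.

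| Interim split (tumor/injury) | Efficacy, d=0.7 | Efficacy, d=0.5 | Futility, d=0.7 | Futility, d=0.5 |
|---|---|---|---|---|
| 35/35 | 0.689 | 0.37 | 0.002 | 0.02 |
| 51/24 (75, none uncertain) | 0.66 | 0.35 | 0.002 | 0.02 |
| 45/21 (half of 90/42) | 0.59 | 0.30 | 0.004 | 0.03 |
| 29/13 (48 × 90/150, 48 × 42/150) | 0.36 | 0.18 | 0.02 | 0.07 |

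The stated 0.69 reproduces at 35/35, and 51/24 comes close. With no discrimination (d=0), the futility chance is 0.5, as the plan says.

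**3. Precision of the comparison after a stop.** The standard error of an AUC difference scales as 1/√n at a fixed split. At 45/21 against 90/42 the interval is √(90/45) = 1.41 times wider. Six months of overrun at the section 4.1 pace (an assumption) adds 75/24 × 6, about 18 patients, giving about 56/26 and √(90/56) = 1.27. Neither ratio depends on the true AUCs.

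**4. Power of the comparison.** Two-sided 5%, assumed correlation 0.3 to 0.7, by paired binormal simulation (correlation between metrics) and by the Hanley-McNeil approximation (correlation between AUC estimates).

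| AUC pair | Method | 90/42 | 45/21 |
|---|---|---|---|
| 0.943 vs 0.829 (pilot, section 3.2) | Simulation | 0.87–0.99 | 0.57–0.81 |
| 0.943 vs 0.829 (pilot, section 3.2) | Approximation | 0.91–0.99 | 0.64–0.88 |
| 0.85 vs 0.75 (assumed) | Simulation | 0.52–0.84 | 0.28–0.51 |
| 0.85 vs 0.75 (assumed) | Approximation | 0.60–0.91 | 0.34–0.64 |

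For nearly equal AUCs (0.943 vs 0.938) power is about 0.05 even at 90/42. The pilot AUCs come from 12 patients scanned with DSC, whereas the trial uses DCE.

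**The case against.** The strongest reply is that the rule matches the formal design. The labelled endpoint, the primary outcome, the biostatistics purpose and the only power calculation all concern tumor-versus-injury discrimination, and stopping for efficiency needs no patient-protection reason. That stands. The rule is not an error against the endpoint; its mismatch is with the primary goal in sections 1.0 and 2.0.

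The efficacy sentence can also be read as a condition for stopping, not a command; only the futility sentence is a flat instruction, and futility is unlikely at the planned effects. This is fair, but the plan's own 0.69 counts every efficacy crossing as a stop.

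A reader might infer four stronger things that the documents do not support:
- *That the stop rests on one MRI perfusion metric.* Context points to MRI perfusion, but section 11.1 also speaks of several t-tests, similar approaches for PET/CT and FDR adjustment across parameters. What can be said is that the governing p-value is unspecified.
- *That a crossing destroys the comparison.* It can still be done in patients already enrolled, with less precision.
- *That type I error is seriously inflated.* It is 0.052 against 0.050, and only if the look is at 48.
- *That the look is still ahead.* With 75 accrued, both candidate counts have been reached. The documents do not say whether it took place.

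The stopping chances (d of 0.5 to 0.7, binormal AUC about 0.64 to 0.69) and the power losses (AUC 0.75 to 0.943) come from different scenarios and must not be multiplied together.

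**Conclusion.** The point holds in this limited form and should be fixed. The boundary arithmetic is right at half information. What is missing is a specified p-value and any link between the stop and the comparison that is the stated primary goal.

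The firmest measure of the loss is precision: an interval about 1.4 times wider after a stop at half accrual, or about 1.27 with the assumed overrun. The power lost ranges from large to negligible, depending on AUCs and correlations that the documents do not fix. The chance of an early efficacy stop is 0.69 at d=0.7 on the plan's figure, and 0.59 (d=0.7) or 0.30 (d=0.5) at 45/21. A futility stop matters mainly if the tested modality does not discriminate; its chance is then 0.5, whatever the other modality can do.

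The 48-versus-75 conflict is a separate, plain contradiction with a small effect on type I error.

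**What to change.** 1. **Settle the interim first.** State whether the look was done and at what count. Then reconcile the two statements in section 11.1: 75 with 0.0088/0.0467 if the look is at half, or boundaries recomputed for the look actually taken (about 0.0017/0.0493 for a look planned at 48 of 150). Do not simply replace 48 by 75 if a look at 48, or at 1 year, has already happened.
2. **Separate the boundary from accrual.** Add after the futility sentence: *Crossing either boundary does not stop accrual, which continues to the planned 150 patients for the PET/CT-versus-MRI perfusion comparison.* State which p-value the boundaries apply to, chosen without reference to outcome data already collected. For a look at half information the printed levels can stay.

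**Cost.** This is a wording change in section 11.1, with no patients or scans beyond the planned 150. It gives up a possible early finish: up to about 75 fewer patients, fewer with overrun, with a chance of about 0.3 to 0.7 at d of 0.5 to 0.7. That is not trivial, but section 14.0 describes both scans as standard tests of minimal risk. The change does not supply a power statement for the AUC comparison, which the plan still lacks.

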To further consider the variation among radiation doses, fractionations and schedules (which may be employed as per the standard of care for the specific tumor type in each patient), a more complicated ANCOVA (analysis of variance with covariates) will be used with the above parameters specified as covariates. If the numbers are small, we will summarize the results descriptively and suggest future research directions. We estimate that 15-25% (21-35 patients of the total) will undergo repeat surgical resection or biopsy to determine the diagnosis. A separate subset analysis will examine for potential differences between lesions diagnosed by pathology vs. lesions diagnosed by clinical and radiological follow up.

Most of the time, the two imaging methods (i.e., MRI perfusion and PET/CT) are expected to yield concordant results (>80%). Therefore, it is meaningful to compare the predictive power of various MRI perfusion measurements and PET/CT measurements. Due to the multiple comparisons needed, an FDR approach will be employed to control for the family-wise error rate. We may further construct a decision rule by combining results from both techniques in the hope of identifying an even more powerful predictive tool, although its feasibility would depend on the exact number of discordant cases and the individual

predictive power (if both MRI perfusion and PET/CT have sufficient predictive power and there are too few discordant cases then the combination may not show significant improvement).

As mentioned above, an interim analysis will be performed after 1 year or accrual of 48 (1/2 of expected total) subjects. Statistical tools may be adjusted at that time point if necessary to account for higher or lower than expected accruals within subgroups. For example, if many more than expected patients have uncertain outcomes or death before diagnosis (without autopsy), then we will may increase the target accrual to compensate.

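### The plan says FDR q-values control the family-wise error rate, which they do not, and its interim rule is written for one p-value without saying which MRI perfusion metric supplies it

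*Combined protocol and SAP*

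**What the plan says.** All of this is in section 11.1 unless noted.

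- **Multiplicity.** "Due to the multiple comparisons needed, a false discovery rate (FDR) approach will be employed to control for the family-wise error rate". The statement returns later in the section: "Due to the multiple comparisons needed, an FDR approach will be employed to control for the family-wise error rate". The version is positive FDR with q-values. No q cut-off and no estimator are given.
- **Interim rule.** "Specifically, this requires the p-value must be <0.0088 at the interim analysis to stop the trial early". The final cut-off is 0.0467, and an interim p-value above 0.50 stops the trial for futility. Under the null, "the early stopping probability is 0.5 for declaring futility and is 0.0088 for declaring significance". That null is that "tumor and necrosis cannot be differentiated by the new imaging method".
- **Which measurement.** The power paragraph names none: "Here we used generic mean/standard deviation ratios because multiple measurements will be examined". The sentence after the interim rule reads "To quantify predictive power of the MRI perfusion package, receiver operating characteristic (ROC) analyses will be used", so MRI perfusion is the natural reading. Section 7.1 lists two MRI perfusion metrics, Vp and Ktrans, and has every metric tested separately.
- **PET/CT against MRI perfusion.** This is the primary goal in section 2.0. In section 11.1 AUCs are compared among the measurements of both modalities, and "the difference between the two AUCs will be calculated and examined whether it is significantly different from 0".

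**The concern.** Two stated properties are at issue.

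First, FDR is the expected share of false claims among the claims made; the family-wise error rate is the chance of any false claim. They coincide only when no metric truly differs. Section 11.1 expects lower readings in radiation injury on both modalities in most scenarios, so some true differences are the planning case.

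Second, the interim rule speaks of a single p-value. With Vp and Ktrans both tested, the plan does not say which one governs, whether one or both must cross, or whether the p-value is adjusted. If the two disagree at the interim look, someone has to decide with the data in view whether the trial stops, and the stated error rate and stopping probabilities depend on that choice.

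**Working it through.** **Step 1: the plan's own figures.** Inputs from section 11.1: one-sided 5%, one look at half information, O'Brien-Fleming shape. Solve P(Z1 ≥ C√2 or Z2 ≥ C) = 0.05 with correlation √0.5 between looks. This gives C = 1.678. Interim p = 1 − Φ(1.678 × 1.414) = 1 − Φ(2.373) = 0.0088; final p = 1 − Φ(1.678) = 0.0467. Both match. For one statistic the null stopping probabilities are 0.0088 and 0.50, also as stated. At effect size 0.7 with 50:25 at the interim, the mean of Z1 is 0.7 × √(50 × 25/75) = 2.858, so P(significance) = Φ(2.858 − 2.373) = 0.69 and P(futility) = Φ(−2.858) = 0.002, again as stated. The boundary is sound for one p-value at half information.

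**Step 2: two metrics under the null.** The correlation between Vp and Ktrans is not in the plan; 0 to 0.8 is assumed. With independence:
- either crosses overall: 1 − 0.95² = 9.75%
- either crosses at the interim: 1 − (1 − 0.0088)² = 1.75%
- both above 0.50: 0.5² = 25%; at least one above 0.50: 1 − 0.5² = 75%

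Simulation over correlation 0 to 0.8 gives:

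| Reading of the rule | Overall type I error | Null interim stop for significance |
|---|---|---|
| One named metric | 5.0% | 0.88% |
| Either metric, unadjusted | 7.5–9.8% | 1.4–1.8% |
| Either metric, Benjamini-Hochberg adjusted | 4.4–5.1% | 0.79–0.88% |
| Both must cross | 0.2–2.4% | at most about 0.3% |

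The unadjusted either-metric error falls to 5.6–6.8% if one metric above 0.50 is enough to stop for futility. Null futility stopping is 25–40% if both must exceed 0.50 and 60–75% if one suffices, against the stated 50%.

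**Step 3: how often the metrics disagree.** Take 45:21 at the interim (half of the plan's 90:42; an assumption) and effect size 0.7 for both metrics. The mean of Z1 is 0.7 × √(45 × 21/66) = 2.649, so each crosses with probability Φ(2.649 − 2.373) = 0.608. With independence, exactly one crosses in 2 × 0.608 × 0.392 = 48% of trials; at correlation 0.8 it is 20%. The trial stops for significance in 71–85% of cases if either counts and in 37–51% if both must.

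**Step 4: FDR against family-wise error.** From the plan: 90:42, effect sizes 0.5 and 0.7, one-sided t-tests. Assumed: q = 0.05, equal correlations of 0 or 0.5, and for Storey a tuning value of 0.5 with the +1 finite-sample estimate. Chance of at least one false claim, 20,000 runs per setting:

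| Family | Benjamini-Hochberg | Storey | Holm |
|---|---|---|---|
| 4 standard lesion metrics (SUV lesion, SUV ratio, Vp, Ktrans), 1–3 truly different | 4–7% | 8–12% | 3–5% |
| All 13 listed (11 PET/CT, 2 MRI perfusion), 3–8 truly different | 10–17% | 15–33% | 3–5% |

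Of the 13, eight are texture or shape features and one is the normal-brain reference SUV.

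**The case against.** **The procedure is identified and only its label is wrong.** This is largely right for the FDR sentence. Positive FDR with q-values is a legitimate choice, and correcting the label changes no analysis. For four metrics the Benjamini-Hochberg excess is small, and if all four truly differ no false claim among them is possible. The 13-metric row depends on features that section 4.2 calls investigational, and the Storey figures depend on an estimator that the plan does not specify. What stands is that a guarantee is stated twice and the method lacks it.

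**The FDR adjustment may already cover the interim.** A reader might infer from the table that the trial runs at nearly 10% type I error. The documents do not support that. Section 11.1 says the FDR step adjusts p-values for the several MRI and PET parameters, and if such adjustment applied to the interim rule, error would be 4.4–5.1% with Benjamini-Hochberg. But no sentence links q-values to the boundary, and Benjamini-Hochberg is itself an assumption. The supportable statement is that the plan does not say.

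**The primary comparison has no single AUC pair.** A reader might call this an error as well. It is a design preference: comparing several pairs under FDR is legitimate, and that is what section 11.1 describes.

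**Timing.** The boundary is right for half information. Section 11.1 also gives 48 subjects as half, while 48/150 is 32%; a look there would put single-metric error at about 5.2%. That inconsistency is a separate matter and does not drive this point.

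**Conclusion.** The point holds in two parts, and both should be corrected.

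The family-wise claim is wrong as written. Its numerical consequence is modest for the four standard lesion metrics and larger if the investigational features join the same family. All sizes rest on an assumed cut-off, estimator and correlation.

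The interim rule is arithmetically correct for one p-value but incomplete for this trial. Depending on the reading, overall error runs from 0.2% to 9.8% and null futility stopping from 25% to 75%, against stated values of 5% and 50%. The evidence does not show that error is inflated; it shows that the stated properties hold only once a governing p-value is fixed. With two metrics that truly differ, the rule leaves the stopping decision open in 20–48% of trials under the assumed 45:21 interim.

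**What to change.** 1. **Multiplicity text.** In both places in section 11.1, drop the family-wise wording, describe the q-values as FDR control, and state the q cut-off and the estimator. Use Holm wherever family-wise control is really wanted.
2. **Interim rule.** Before the interim look, name one metric whose unadjusted one-sided t-test governs the interim efficacy, futility and final cut-offs. Then 0.0088, 0.0467 and the stated null stopping probabilities hold unchanged. Alternatively, split alpha between Vp and Ktrans: halving gives about 0.0044 and 0.0234 each, to be re-derived exactly at 2.5% per metric. In that case define futility for two metrics and restate the stopping probabilities.
3. **AUC comparison.** Report PET-minus-MRI AUC differences as estimates with bootstrap confidence intervals, with q-values across pairs as planned. Do not make this conditional on an MRI t-test. With assumed AUCs of 0.80 for PET and 0.55–0.60 for MRI, such a gate cuts power for the difference from 92–100% to 20–52%, exactly when the modalities differ most. State whether the comparison is made at half size if the trial stops early. Under assumed AUCs of 0.75 against 0.80–0.85, the 95% interval is about ±0.11 to 0.15 at 45:21, against ±0.08 to 0.10 at 90:42.

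The cost is SAP text and one decision, with no new data unless enrolment continues past an early crossing. The downside is that fewer metrics can carry the confirmatory claim, or each faces a stricter cut-off.
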